3.1 Selection of Patients

The target population for this study is patients with stage IV breast, NSCLC lung cancers and Sarcoma.

This will be a multi-center trial conducted by Mays Cancer Center. At Mays Cancer Center, patients will be recruited by the clinical team in the Breast Center; lung center and sarcoma center. Potential patients may be referred to the Principal Investigator, [name], at [contact].

Eligibility will be evaluated by the study team according to the following criteria. Eligibility waivers are not permitted. Subjects must meet all of the inclusion and none of the exclusion criteria to be registered to the study. Study treatment may not begin until a subject is registered. Please refer to Section 11 for complete instructions regarding registration procedures.

Inclusion Criteria

- Stage IV breast cancer, stage IV NSCLC, stage IV sarcoma
- ECOG PS 0-2
- Measurable disease
- No more than 4 prior chemotherapeutic regimens for metastatic disease
- Patients must be \geq 18 years.
- Patients may not have received Eribulin or lenvatinib previously
- Patients must have a life expectancy of greater than 12 weeks.
- Patients may have had a prior diagnosis of cancer if it has been $>$ 5 years since their last treatment and are considered free of disease.
- Patients must have normal organ and marrow function as defined below:
 - Leukocytes \geq 3,000/ μ L
 - Absolute neutrophil count \geq 1,500/ μ L
 - Platelets \geq 100,000/ μ L
 - Child Pugh score \leq 10
- Patients must be able to swallow and retain oral medication.
- All patients must have given signed, informed consent prior to registration on study.

Exclusion Criteria

- Women who are pregnant or lactating are not eligible for study treatment.
- Patients who are undergoing concomitant radiotherapy are NOT eligible for participation.
- Patients who are receiving any other investigational agents or concurrent anticancer therapy are NOT eligible for participation. Previous systemic treatment and/or radiation therapy is allowed with a 14 day washout period prior to registration.
- Lesions that have been radiated previously cannot be considered target lesions
- Prior treatment related side effects must have resolved to $<$ Grade 2 severity per Common Terminology Criteria for Adverse Events (CTCAE version 4.03), except alopecia and infertility.

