6.0 Study Parameters

Procedures	Screening & Baseline	Cycle 1	Every cycle ²	Every 2 cycles or at study termination	End of study visit ⁷	Follow-Up ⁶
Tissue procurement ¹	X			X ⁵		
Informed consent	X					
Eribulin administration			X (Days 1 & 8)			
Lenvatinib			X once daily (starting on day 2 of cycle 1)			
Medical history ³	X		X		X	
Physical exam ³	X		X		X	
CBC w/ diff	X ³		X		X	
Comprehensive chemistry panel	X ³		X			
TSH	X		X			
Serum pregnancy test	X					
EKG	X		X ¹⁰			
Blood draw for micro RNA assay ⁹		X			X	

Procedures	Screening & Baseline	Cycle 1	Every cycle ²	Every 2 cycles or at study termination	End of study visit ⁷	Follow-Up ⁶
Urine analysis ¹¹	X			X		
Imaging ⁸	X ⁴			X		
Toxicity assessment			X			
Biopsy				X ⁵		
Survival status						X

¹Archival tissue or a fresh biopsy will be required to procure tissue for study purposes. Biopsy does not need to be repeated for study purposes if archived tissue is available.

Tissue procurement is voluntary

²A cycle is defined as 3 weeks or 21 days (+/- 3 days). Eribulin will be given on cycle days 1 and 8 and lenvatinib starting on day 2 of cycle one and then continuously.

³Pre-study laboratory tests, medical history, and physical exam (including performance status and review of systems) must be completed within 28 days prior to registration.

Pre-study CBC and CCP will be repeated on day 1 prior to treatment administration.

⁴Pre-study imaging must be performed within 28 days prior to registration.

⁵At the initiation and completion of study treatment (or at the time of early withdrawal), tissue samples should be obtained for correlative studies. This is voluntary and will only be done on patients who consent to it.

⁶Patients will be followed every 6 months, at the time of routine clinic visit or via phone, until death, to document disease progression and survival.

⁷Within 30 days of last dose of study medications.

⁸Imaging modality is left to the discretion of the investigator. However the same imaging modality should be used every two cycles to assess disease status.

⁹Blood samples for microRNA assay will be collected on Cycle 1, Day 1 and at the end of treatment.

¹⁰Repeat EKG with every cycle in patients with congestive heart failure, bradyarrhythmias, or those who are taking drugs known to prolong the QT interval, including Class Ia and III antiarrhythmics.

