8.2 Data analysis

Data will be analyzed by the PI and [name] using Stata statistical software. We will provide descriptive statistics and confidence intervals for all variables of interest for which data are collected.

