8.3 Correlative science

Objective. To quantify serum levels of microRNAs pre- and post-treatment, with the goal of correlating levels with patient response to treatment.

RNA isolation. RNA will be isolated using the mirVanaTM miRNA Isolation Kit (Ambion) and quantified using a Nanodrop spectrophotometer. RNA quality will be determined on an Agilent 2100 Bioanalyzer.

miRNA expression profiling by NGS. We will use the HiSeq 2000 Sequencing System (Illumina) at the GCCRI Genomics Facility to measure miRNA expression profiles. Samples will be barcoded to allow multiplex sequencing and subjected to a second round of Q/C.

Data analysis. Adaptor sequences will be removed and reads of the length ≤ 15 or ≥ 30 are removed as they are not likely to originate from mature miRNAs. Duplicate reads will be removed with the remaining unique reads stored in FASTA format along with the read count. Unique reads will be aligned to the reference human genome (hg19) using the Bowtie short read aligner (0.12.9). Reads mapped to known miRNA loci as defined by miRbase (v21) will be kept for expression profiling. miRNA expression will be derived from counting reads perfectly matching known miRNA loci, normalized to the total number of uniquely mapped reads per sample.

Expected results. Expression profiles of serum miRNAs in 10 responders and 10 non-responders, which can then be compared by t-test to identify differentially expressed miRNAs that correlate with patient response to treatment.

Blood samples for microRNA assay will be collected on Cycle 1, Day 1 of treatment, and at the end of treatment. QIAGEN PAXgene Blood RNA tubes will be used to collect the samples.

Blood samples will be sent to [name] lab:

[name] ([contact])
Greehey Children's Cancer Research Institute
UT Health Science Center at San Antonio
[name]
[name]
T [contact]

Tissue specimens from before and after treatment will be stained for markers of both angiogenesis and of hypoxia, CD-36 and carbonic anhydrase 9 (CA9) respectively, to see if the combination is effective at reducing hypoxia and the effects on angiogenesis. We will also look at the effects on reversal of EMT by performing IHC for E-cadherin, N-cadherin and vimentin to see if there is a reversion with treatment as has been seen in vitro and in animal models.

All IHC will be performed in [name] lab:

UT Health San Antonio
[name]
[name]
[contact]

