11.1.2 Registering a Patient for the Safety run in Portion of the Study

For potential patients for the phase I portion of this study, please email the UT Health San Antonio Nurse/Research Coordinator *prior to consenting a patient* to determine whether a slot is available on the current cohort. An email confirming the reservation and expiration date will be sent by the UT Health San Antonio Nurse/Research Coordinator. In order for registrations to be processed efficiently, study teams are asked to inform the UT Health San Antonio Nurse/Research Coordinator of the date and time that the patient will need to be registered. Detailed instructions and project coordinator contact information regarding registration procedures will be provided separately from this protocol.

To register a patient, please complete and submit the following items to confirm eligibility and receive a subject identification number:

- Eligibility checklist (signed and dated by the treating physician)
- Signed and dated informed consent document
- Pathology Report

Affiliates sites are required to de-identify, scan, and e-mail the following source documents in order to confirm eligibility prior to registration for phase I patients:

- Complete medical and surgical history, current medications, history of clinically significant infections, and physical exam [including weight, height, ECOG PS, vital signs (pulse, temperature, respiratory rate, blood pressure, oxygen saturation)]
- Lab results (baseline CBC w/diff, baseline CMP)
- Documentation that archival tissue is available or documentation that a biopsy will be done
- Negative serum pregnancy test (if applicable)
- Copy of baseline imaging report

UT Health San Antonio study teams are NOT required to submit a separate email for UT Health San Antonio participants, provided that the required documentation listed above is readily available in the patient's electronic medical record (EMR). However, any information that is not available in the EMR must be de-identified and retained in the subject's research record.

The Nurse/Research Coordinator will review all source documentation required to confirm eligibility with the PI. Once confirmed, the Nurse/Research Coordinator will register the patient, assign a subject identification number, provide a cohort assignment, and send a confirmation of registration to the study team. Registration will then be complete and the patient may begin study treatment.

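### The baseline specimen for the before/after staining can be an old archival block, so a marker change could reflect earlier therapy or another lesion rather than the combination

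*Combined protocol and SAP*

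**What the plan says.** - **The comparison.** Sections 8.3 and 16.0: "Tissue specimens from before and after treatment will be stained for markers of both angiogenesis and of hypoxia". The markers are CD-36 and CA9, then E-cadherin, N-cadherin and vimentin for EMT. The purpose is "to see if the combination is effective at reducing hypoxia and the effects on angiogenesis".
- **Baseline source, footnote 1 of 6.0.** Either archival tissue or a fresh biopsy is acceptable, and "Biopsy does not need to be repeated for study purposes if archived tissue is available". In the schedule, tissue procurement is marked at screening, but the separate biopsy row is marked only in the column for every two cycles or study termination.
- **Baseline timing, footnote 5 of 6.0.** Samples for correlative studies should be obtained when study treatment starts and when it ends. It adds: "This is voluntary and will only be done on patients who consent to it".
- **Registration check, 11.1.2** (run-in patients at affiliate sites): "Documentation that archival tissue is available or documentation that a biopsy will be done".
- **Prior therapy, 3.1.** "No more than 4 prior chemotherapeutic regimens for metastatic disease", and "Previous systemic treatment and/or radiation therapy is allowed with a 14 day washout period prior to registration".
- **Analysis, 8.2.** "We will provide descriptive statistics and confidence intervals for all variables of interest for which data are collected". Neither 8.2, 8.3 nor 16.0 has a rule on specimen age, lesion or therapy given between the specimen and study entry.

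**The concern.** A before/after difference isolates a treatment only if little else happened between the two samples. Footnote 1 permits a baseline block cut before some or all of the patient's earlier treatment for metastatic disease. The difference then adds together the effects of that treatment, disease evolution, any difference between lesions, and the study drugs. Hypoxia, angiogenesis and EMT markers could plausibly move with any of these. The trial has one arm, so no comparison group carries the same background change.

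At stake is the interpretation of the tissue results: a shift in CA9 or vimentin could be reported as an effect of the combination when part or all of it arose before the first study dose. It could equally hide a real effect if the earlier drift ran the other way.

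**Working it through.** **1. Is there a plan figure to reproduce?** None for the tissue analysis. The only design figures in section 8 belong to the response-rate test (8.1.2: N = 30, p0 = 0.20, p1 = 0.40, reject at 10 or more responses). The exact binomial tails are P(X ≥ 10 | 30, 0.20) = 0.0611 and P(X ≥ 10 | 30, 0.40) = 0.8237, both as stated. Neither depends on tissue.

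**2. The provisions side by side.**

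| Question | Footnote 1 (6.0) | Footnote 5 (6.0) | 8.3 and 16.0 |
|---|---|---|---|
| When is the baseline specimen taken? | Any time, if archived | Start of study treatment | Before treatment, no window |
| Must it follow the last prior therapy? | Not stated | Implied by the timing | Not stated |
| Same lesion as the later sample? | Not stated | Not stated | Not stated |

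Footnote 5 does not withdraw the archival option, and footnote 1 does not exclude the correlative work. A site following footnote 1 can supply an old block and comply. The request in 16.0 for unstained slides from pathology is compatible with a stored block.

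**3. How much therapy can lie in between?** From none to four chemotherapy regimens for metastatic disease (3.1). That cap does not count adjuvant treatment, non-chemotherapy systemic treatment or radiation.

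**4. Direction of the arithmetic.** Let δ be the true mean effect of the combination, f the share of pairs whose baseline predates prior therapy, and d the mean drift between that specimen and study entry in those pairs. If all pairs are summarised together:

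mean observed change = δ + f × d

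With δ = 0, f = 0.5 gives d/2 and f = 1 gives d. The documents give neither f nor d.

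**5. Illustration only.** Assume no drug effect (δ = 0), all pairs carrying the drift (f = 1), drift in units of the SD of the paired difference, and a two-sided 95% interval from a paired t analysis. None of these is in the plan. The chance that the interval excludes zero, from the noncentral t distribution with noncentrality drift × √n, is:

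| Pairs | Drift 0 | 0.2 SD | 0.5 SD | 0.8 SD |
|---|---|---|---|---|
| 10 | 0.05 | 0.088 | 0.293 | 0.616 |
| 20 | 0.05 | 0.136 | 0.565 | 0.924 |
| 30 | 0.05 | 0.185 | 0.754 | 0.988 |

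More pairs make the false signal likelier, because the problem is bias and not imprecision.

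**The case against.** The best reply is that footnote 5 addresses this analysis specifically and asks for tissue when treatment starts. Footnote 1 could then be read as concerning enrolment only: section 15.0 requires biopsy-proven disease, and 11.1.2 uses archival availability as a registration check. On that reading the protocol has two poorly aligned footnotes and no plan to use old blocks. This stands as a possible reading. It does not remove the point, because footnote 1 speaks of study purposes without exception, the biopsy row has no screening mark, and footnote 5 is voluntary.

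Several limits also stand:

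- An archived block may postdate the last regimen, and a patient may have had no prior regimen. Four is the ceiling, not the expectation.
- That lesions will differ is inferred from the lack of a same-lesion rule. No text says they will.
- 8.3 states a purpose. It sets no test, threshold or decision, and no text says archival and fresh pairs will be pooled.
- If both kinds of pair exist, comparing them would give a rough, non-randomised idea of the drift, so it is not wholly beyond estimation.
- The staining is not among the objectives in the synopsis or 3.0, and taking part is voluntary.

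A reader might infer that the plan commits to crediting changes from earlier regimens to the combination. The documents do not say so; they leave the way open to it.

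**Conclusion.** The point holds as a gap in a correlative analysis. Footnotes 1 and 5 of section 6.0 conflict on the baseline specimen. Under footnote 1, a before/after change in CD-36, CA9 or the EMT markers could reflect prior therapy, disease evolution or lesion instead of the study drugs, and a single-arm design does not separate them.

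The size is unknown. The f × d expression and the table above show how the bias would act under assumed values; they do not estimate it. The conclusion assumes that at least some patients supply a block that predates prior therapy, which the text permits but does not quantify.

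It would be wrong to infer that the trial's main result is compromised: the response-rate test in 8.1.2 uses no tissue data. This is a cheap improvement, not a flaw in the primary design.

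**What to change.** 1. In 6.0, reconcile footnotes 1 and 5 so that it is clear which specimen is the baseline for the staining and which merely meets the tissue requirement at screening.
2. In 8.3 and 16.0, limit the comparison attributed to the combination to pairs whose baseline specimen was taken after the last prior anticancer therapy, from the same site where possible.
3. Report the remaining archival pairs separately and descriptively, without attributing change to the combination.
4. Record specimen date, specimen site and date of last prior therapy, and report the number of pairs of each kind.

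**Cost.** Wording changes and three data items; no extra biopsy. The 14-day washout check in 3.1 already needs the date of last systemic or radiation therapy, so that item may only have to be carried into the analysis data. The downside is fewer pairs in the attributed comparison. In a voluntary collection there may be very few, in which case the results should be described as such and no effect claimed.

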9.0 Adverse Events Reporting

Adverse event data collection and reporting, which are required as part of every clinical trial, are done to ensure the safety of subjects enrolled in the studies as well as those who will enroll in future studies using

similar agents. Subjects must be carefully monitored for AEs. This monitoring also includes clinical laboratory tests. Adverse events should be assessed in terms of their seriousness, intensity, and relationship to the study drug, or other chemotherapy/treatment. Adverse events are reported in a routine manner at scheduled times during a trial. Additionally, certain adverse events must be reported in an expedited manner to allow for optimal monitoring of patient safety and care.

All patients experiencing an adverse event, regardless of its relationship to study drug, will be monitored until:

- the adverse event resolves or the symptoms or signs that constitute the adverse event return to baseline;
- any abnormal laboratory values have returned to baseline;
- there is a satisfactory explanation other than the study drug for the changes observed; or
- death occurs.

Therapeutic monitoring should be performed following dose modification in a manner consistent with the local clinical standard of care. In general, subjects should be closely monitored for side effects of all concomitant medications regardless of the path of drug elimination.

9.2 Definitions & Descriptions

9.2.1 Adverse event (AE)

An adverse event (AE) is any untoward medical occurrence in a patient receiving study treatment and which does not necessarily have a causal relationship with this treatment. An AE can, therefore, be any unfavorable and unintended sign (including an abnormal laboratory finding), symptom, or disease temporally associated with the use of an experimental intervention, whether or not related to the intervention. A "drug-related toxicity" includes as events, any toxicity considered related, probably related, or possibly related to study drugs. Toxicities clearly not related to the drug, such as disease progression, environmental, unrelated trauma may not be considered "drug related toxicity".

9.2.2 Severity of AEs

All adverse events will be graded according to the NCI Common Terminology Criteria for Adverse Events (CTCAE) version 4.03. The CTCAE v. 4.03 is available at
http://evs.nci.nih.gov/ftp1/CTCAE/CTCAE_4.03_2010-06-14_QuickReference_5x7.pdf

If no CTCAE grading is available, the severity of an AE is graded as follows:

Mild (grade 1): the event causes discomfort without disruption of normal daily activities.

Moderate (grade 2): the event causes discomfort that affects normal daily activities.

Severe (grade 3): the event makes the patient unable to perform normal daily activities or significantly affects his/her clinical status.

Life-threatening (grade 4): the patient was at risk of death at the time of the event.

Fatal (grade 5): the event caused death.

9.2.3 Serious Adverse events

All SAEs, regardless of attribution, occurring during the study or within 30 days of the last administration of study drug must be reported upon discovery or occurrence. Additional expedited or routine reporting may be required, depending on the nature of the SAE. A “serious” adverse event is defined in regulatory terminology as any untoward medical occurrence that:

- Results in death. If death results from (progression of) the disease, the disease should be reported as the event (SAE) itself.
- Is life-threatening. The patient was at risk of death at the time of the event; it does not refer to an event that hypothetically might have caused death if it were more severe.
- Requires in-patient hospitalization or prolongation of existing hospitalization for ≥ 24 hours.
- Results in persistent or significant disability or incapacity.
- Is a congenital anomaly/birth defect.
- Is an important medical event.
- Any event that does not meet the above criteria, but that in the judgment of the investigator jeopardizes the patient, may be considered for reporting as a serious adverse event. The event may require medical or surgical intervention to prevent one of the outcomes listed in the definition of “Serious Adverse Event”. Examples: allergic bronchospasm requiring intensive treatment in an emergency room or at home; convulsions that may not result in hospitalization; development of drug abuse or drug dependency.

9.2.4 Exceptions to the Definition of SAE

Certain hospitalizations or prolongation of hospitalizations should not be considered SAEs, including those that meeting the following criteria:

- An admission resulting in a hospital stay of less than 12 hours.
- An admission that is pre-planned (i.e. elective or scheduled surgery arranged prior to the start of the study).
- An admission that is not associated with an AE (i.e. social hospitalization for purposes of respite care)

9.2.5 Unanticipated Problems Involving Risks to Subjects or Others (UPIRSO)

A UPIRSO includes events that meet ALL of the following criteria:

- Are unanticipated in terms of nature, severity, or frequency
- Place the research subject or others at a different or greater risk of harm, AND
- Are deemed to be related or possibly related to participation in the study

10.0 Adverse event reporting

Steps to determine if expedited reporting is required

This includes all events that occur within 30 days of the last dose of protocol treatment. Any event that occurs more than 30 days after the last dose of treatment and is attributed (possibly, probably, or definitely) to the agent(s) must also be reported accordingly.

Identify the type of adverse event using the NCI CTCAE v 4.03.

Grade the adverse event using the NCI CTCAE v 4.03.

Determine whether the adverse event is related to the protocol therapy.

Attribution categories are as follows:

Definite: AE is clearly related to the study treatment (attribution should be separated by each study drug)

Probable: AE is likely related to the study treatment (attribution should be separated by each study drug)

Possible: AE may be related to the study treatment (attribution should be separated by each study drug)

Unrelated: AE is clearly NOT related to the study treatment (attribution should be separated by each study drug)

Determine the prior experience of the adverse event. Expected events are those that have been previously identified as resulting from administration of the specific agent. An adverse event is considered unexpected, for expedited reporting purposes only, when either the type of event or the severity of the event is not listed in:

- the current protocol, the drug package insert;
- or the current Investigator's Brochure.

